11.3 Additional Efficacy Analyses

11.3.1 Hemoglobin Maintenance

11.3.1.1 Hemoglobin long-term Maintenance

Hemoglobin long-term maintenance will be assessed by:

- Mean change in hemoglobin averaged over 8 weeks of treatment at Weeks 44-52 without rescue therapy within 6 weeks prior to and during this 8-week evaluation period.
- Mean change in hemoglobin averaged over the Week 96- 104 of treatment without rescue therapy within 6 weeks prior to and during this 8-week evaluation period.
- Change in hemoglobin at each of the selected post-dosing time points
- Proportion of subjects with hemoglobin ≥ 10 g/dL averaged over 36 to 44, 44 to 52, and the Week 96- 104 without rescue therapy within 6 weeks prior to and during this 8-week evaluation period.
- Proportion of subjects with hemoglobin within 10-12 g/dL averaged over 36 to 44, 44 to 52, and the Week 96- 104 without rescue therapy within 6 weeks prior to and during this 8-week evaluation period.
- Hb response during Weeks 28 and 36 regardless of use of rescue therapy
- Hb change from BL to the average Hb value of Weeks 28 to 36, 44 to 52, and 96 to 104 of treatment regardless of the use of rescue therapy

The change in hemoglobin, will be analyzed using MMRM model with baseline hemoglobin as a covariate, treatment group, visit, the interaction of treatment and visit, and stratification factors except mean qualifying screening hemoglobin (≤ 10.5 vs. >10.5 g/dL) as factors.. The same strategy as that used in MMRM in Section 11.1.2.1 will be used to choose variance covariance. Data up to visit of Week 52 will be included in the analyses. The estimates for

the difference of change from baseline in Hemoglobin for Week 28 to 36 and 44 to 52 between the two treatment groups will be generated from an estimate statement. The mean change in Hb averaged over 8 weeks of treatment at Weeks 96-104 will be analyzed using the MI analyses as the one for the primary efficacy endpoint of US-submission.

The proportion of subjects with hemoglobin within 10-11 g/dL in US and 10-12 g/dL in Ex-US will be analyzed using logistic regression model including baseline hemoglobin as a covariate and treatment group and stratification factors except mean qualifying screening hemoglobin (≤ 10.5 vs. >10.5 g/dL) as fixed effects.

Hemoglobin change from baseline to the average hemoglobin value of the Week 96 to 104 weeks of treatment will be analyzed using an MI ANCOVA model with baseline hemoglobin as a covariate, and treatment group and stratification factors except mean qualifying screening hemoglobin (≤ 10.5 vs. >10.5 g/dL) as fixed effects, using the Hb mean from the non-missing weeks.

In this study, there are patients in whom roxadustat dose frequency needed to be reduced to BIW or QW as part of their dose reduction below the lowest possible TIW dose of 20 mg TIW during treatment, to evaluate Hb maintenance, the following summary will be provided for these subgroups of subjects treated on BIW or QW (including any frequency $<QW$) for longer than 8 weeks (i.e., ≥ 56 days):

- Average Hb values over time for every 4-8 weeks after the initiation of BIW or QW
- Average weekly dose over time for every 4-8 weeks after the initiation of BIW or QW

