Although the treatment of anemia in CKD and ESRD is thought to contribute positively to a patient's quality of life, several studies in subjects with ESRD and NDD-CKD have shown higher mortality or trends in that direction in the higher-dosed ESA-treated cohorts when the protocol objective was to treat one of the cohorts to high, almost normal target Hb levels (Besarab et al., 1998; Drueke et al., 2006; Singh et al., 2006). An ESA dose relationship to mortality has been reported in a review of the USRDS database (Zhang et al., 2004) of ESRD patients who received higher ESA doses, particularly in those more anemic (ie, Hb < 11 g/dL). The FDA has recognized these excess morbidity and mortality risks (FDA, 2007). Updated product labeling for the approved ESAs in 2007 include a boxed warning of greater risk of death and CV events when ESAs are administered to target high Hb concentrations ( $\geq 13.5$  g/dL) compared with lower Hb targets. The FDA also acknowledged the potential off-target effect of ESAs contributing to excess mortality due to CV events and thrombosis (Unger, 2010). The currently approved ESA labeling directs prescribers to target Hb levels of 10 to 11 g/dL in the US and 10 to 12 g/dL outside the US. The literature on this topic, including meta-analyses, supports the view that the AEs associated with ESAs are typically observed when high doses are administered (Zhang et al., 2004; Unger, 2007; Szczech, 2008; Fishbane and Besarab, 2007; Besarab et al., 2009). Posthoc analyses of three major RCTs, (Kilpatrick et al., 2008; Szczech, 2008; Solomon et al., 2010) NHCT, CHOIR, and TREAT, indicates that outcomes correlate with "achieved" and not "target" Hb levels.

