### 3.2.3 Additional Evaluation of Efficacy

The additional efficacy evaluations in this study are:

- Hb Maintenance:
  - Hemoglobin Long-Term Maintenance: Mean change from BL in Hb averaged over 8 weeks of treatment at Weeks 44 to 52 without rescue therapy within 6 weeks prior to and during this 8-week evaluation period
  - Mean change from BL in Hb averaged over the final 8 weeks of treatment, without rescue therapy within 6 weeks prior to and during this 8-week evaluation period
  - Change from BL in Hb at each of the selected postdosing time points
  - Proportion of subjects with 10-12 g/dL averaged over Weeks 28 to 36, 44 to 52, and the final 8-weeks of treatment without rescue therapy within 6 weeks prior to and during this 8-week evaluation period
  - Hb response during Weeks 28 and 36 regardless of use of rescue therapy
  - Hb change from BL to the average Hb value of Weeks 28 to 36, 44 to 52, and the final 8 weeks of treatment regardless of the use of rescue therapy
- Iron Supplement:
  - Requirement for IV iron supplementation
  - Mean monthly IV iron (mg) per subject during Weeks 37 to 52 and Week 53 to EOS
  - Mean monthly oral iron (mg) use per subject during Weeks 1 to 36, Weeks 37 to 52, and Weeks 53 to EOS
  - Requirement for only oral iron supplementation
- Hospitalizations:
  - Occurrence (number) of hospitalizations
  - Proportion of subjects hospitalized
  - Number of days of hospitalizations per patient-exposure year (PEY)

- Missed Dialysis:
  - Occurrence (number) of missed dialysis sessions
  - Proportion of subjects with missed dialysis sessions
  - Number of days of missed dialysis sessions per patient-exposure year (PEY)
- Rescue Therapy Use:
  - Proportion of subjects who receive RBC transfusions
  - Number of RBC packs per patient-month exposure to study medication
  - Having received rescue therapy [composite of RBC transfusions and rescue ESA]
- Changes in Cholesterol Levels:
  - Change from BL at each of the selected treatment time points in:
    - Total cholesterol
    - Low-density lipoprotein/high-density lipoprotein ratio
    - Non-HDL cholesterol
  - Proportion of subjects achieving LDL target of < 100 mg/dL averaged over Weeks 12 to 28 of treatment
- Blood Pressure Effect:
  - Proportion of subjects achieving BP treatment goal in ESRD subjects (predialysis systolic BP < 140 mmHg and diastolic BP < 90 mmHg) averaged over Weeks 12 to 28
  - Time to a treatment-emergent AE of hypertension

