### 4.5.3 Dose Adjustment

#### 4.5.3.1 Roxadustat Arm

During the Treatment Period, roxadustat dose adjustment will be made according to the dose adjustment algorithm in Appendix 2, in order to maintain a Hb level of approximately 11 g/dL. Roxadustat dose adjustments are permitted from Week 4 onwards, and every 4 weeks thereafter (eg, Week 4, Week 8, Week 12); however, dose may be adjusted between two prespecified windows (eg, anytime between Week 4 and Week 8 visits, Week 8 and Week 12 visits) if the following two criteria are met:

- No dose adjustment has been made in last 4 weeks,
- Hemoglobin (Hb) < 9.0 g/dL.

Subjects on HD or PD or HHD randomized to roxadustat will take doses TIW for the entire duration of the Treatment Period. If a subject requires < 20 mg TIW (ie, < 60 mg per week) to maintain a Hb level of approximately 11 g/dL, the dosing frequency should be reduced in a step-wise fashion e.g. TIW to BIW, BIW to QW, QW to Q-2 Week etc.

In this study, a rate of rise of Hb > 2 g/dL within 4 weeks or a Hb level of  $\geq$  13 g/dl at any time would be considered as excessive haematopoiesis. For a rate of rise of Hb > 2 g/dL within 4 weeks, dose should be reduced by one dose step and for a Hb value  $\geq$  13.0 g/dL, the dose should be on hold until Hb drops < 12.0 g/dL per guidelines provided in the protocol (Appendix 2). When roxadustat will be resumed, the dose will be reduced by one dose step.

Dose adjustments or temporary dose holds for excessive hematopoiesis can occur at any time during the Treatment Period. Any dose adjustment will reset the dose-adjustment window to every 4 weeks thereafter (eg, dose adjustment for a qualified reason at Week 6 leads to next dose adjustment at Week 10). If a dose adjustment review is scheduled on Week 22, then the next dose adjustment review will be scheduled on Week 28, since there is no scheduled visit on Week 26.

Prescribed dose must not exceed the maximum allowable dose of 3.0 mg/kg/dose or 400 mg per dose, whichever is lower. For dose adjustment purposes, post-dialysis weight (dry-weight) should be used. If the post-dialysis weight of the current visit is not available at the time of dose adjustment, post-dialysis weight of the prior dialysis session or last recorded post-dialysis weight may be used.

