#### **4.5.3.2 Active Control (Epoetin alfa) Arm**

Epoetin dose adjustments during the Treatment Period should be based on country-specific epoetin alfa Package Insert or SmPC.

In subjects on PD or HHD, if receiving epoetin alfa subcutaneously, the dose and frequency may be determined by the Investigator per local standard of care.

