4.3 Additional Evaluation of Efficacy

The additional efficacy evaluations in this study are:

- **Hemoglobin Maintenance:**
 - Hemoglobin long-term Maintenance: Mean change from baseline in hemoglobin averaged over 8 weeks of treatment at Weeks 44-52 without

- rescue therapy within 6 weeks prior to and during this 8-week evaluation period.
- Mean change from baseline in hemoglobin averaged over the Week 96 to 104 of treatment, without rescue therapy within 6 weeks prior to and during this 8-week evaluation period.
 - Change from baseline in hemoglobin at each of the selected post-dosing time points.
 - Proportion of subjects with Hb ≥ 10 g/dL averaged over Weeks 28 to 36, 44 to 52, and 96 to 104 of treatment without rescue therapy within 6 weeks prior to and during the evaluation periods.
 - Proportion of subjects with Hb ≥ 10 g/dL averaged over Weeks 28 to 36, 44 to 52, and 96 to 104 of treatment regardless of rescue therapy
 - Proportion of subjects with Hb within 10-12 g/dL averaged over Weeks 28 to 36, 44 to 52, and 96 to 104 of treatment without rescue therapy within 6 weeks prior to and during these 8-week evaluation periods.
 - Proportion of subjects with Hb within 10-12 g/dL averaged over Weeks 28 to 36, 44 to 52, and 96 to 104 of treatment regardless of rescue therapy use.
 - Hemoglobin change from baseline to the average hemoglobin value of weeks 28 to 36, 44 to 52, and 96 to 104 of treatment regardless of the use of rescue therapy.
- **Iron Supplement:**
 - Time to and Proportion of subjects who has requirement for IV iron supplementation.
 - Mean monthly IV iron (mg) per subject during weeks 28-52, 53-104, and 105 -EOT.
 - Mean monthly oral iron (mg) use per subject during 28-52, 53-104, and 105 - EOT.
 - Proportion of subjects who has Requirement for only oral iron supplementation (Week 1 to 52).
 - **Hospitalizations**
 - Time to first hospitalization (% of subjects) up to Week 52, 7 days after Last Dose. Time to first hospitalization or skilled nursing facility (% of subjects) up to Week 52, 7 days after Last Dose.
 - Number of days of hospitalizations due to AE per subject-exposure year (PEY)
 - Number of days in hospital or skilled nursing facility due to AE per patient-year exposure (PEY)
 - Number of days in medical-facility (hospital, skilled nursing facility, emergency room, or overnight observation) due to AE per patient-year exposure (PEY)

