11.2.2.1 Proportion of Hemoglobin Responders

- US: Proportion of subjects with mean hemoglobin level during the evaluation period defined as Week 28 until Week 52 ≥ 10.0 g/dL, and patients with mean hemoglobin level between Hb 10-12 g/dL.
- Ex-US: Proportion of subjects with mean Hb between range of 10.0 to 12.0 g/dL without having received rescue therapy within 6 weeks prior to and during this 8-week evaluation period.

The hypothesis to be tested for the efficacy analysis is:

H0: Hemoglobin response rate for subjects in the roxadustat group - hemoglobin responder rate for subjects in the Epoetin group $\leq -15\%$

Versus

H1: Hemoglobin response rate for subjects in the roxadustat group - hemoglobin responder rate for subjects in the Epoetin group $> -15\%$.

A 2-sided 95% confidence interval for the difference of 2 responder rates (roxadustat – ESA) based on the Miettinen & Nurminen approach adjusting for treatment group and stratification factors will be calculated and non-inferiority will be declared if the lower bound of the 95% CI is greater than -15%.

Subjects who dropped out from the study before week 28 will be treated as non-responder.

11.2.2.2 Change from Baseline in LDL Cholesterol Averaged over Weeks 12 to 28

The change from baseline in LDL cholesterol will be analyzed and compared between the 2 treatment groups using MMRM model with baseline LDL cholesterol as a covariate and treatment group, visit, the interaction of treatment and visit, and the above mentioned stratification factors as fixed effects. The same strategy as that used in MMRM for Hb will be used to choose variance covariance structure. Data up to visit of Week 52 will be included in the model. The estimates for difference of LDL Cholesterol averaged over Weeks 12 to 28 between the two treatments groups will be generated from an estimate statement from Visit Week 12 to 28. Superiority will be declared if the upper bound of the 2-sided 95% confidence interval of the difference between roxadustat and active control does not exceed 0.

Baseline, LDL, is defined as the last available value obtained prior to the first dose of study drug.

11.2.2.3 Hemoglobin change from baseline to the average level during the Week 18 to 24 for Subjects with CRP > ULN

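### The explicit efficacy factor list in SAP 11.1.1.1 omits region, against the protocol's primary model and SAP 5.4; a smaller slip in SAP 11.3.1.1 models 10-11 g/dL for an endpoint defined as 10-12 g/dL

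*SAP*

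**What the plan says.** **Region.** The protocol synopsis, 4.2 and 9.2 all list geographical region (US vs Ex-US) as a randomization factor, with screening Hb, cardiovascular history and prior epoetin dose. (The lead-in to 9.2 says three factors, but the list under it has four.) Protocol 9.4.3.1 puts the randomization factors other than screening Hb into both the primary MI-ANCOVA and the MMRM, so region is in both.

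The SAP is not consistent on this:
- SAP 5.4 says the randomization factors will be used in all applicable models, and that the factors to include are these plus incident dialysis (up to 4 months vs longer).
- SAP 5.1 announces four randomization factors and lists three; region is the missing one.
- SAP 11.1.1.1 sets out the factors for the efficacy analyses: screening Hb (only for endpoints that are not Hb-related), cardiovascular history, epoetin dose and incident dialysis. Region is not there.
- SAP 11.1.1.2, the MMRM for the EU primary endpoint, refers only to the stratification factors in general terms.

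**Band.** The model sentence in SAP 11.3.1.1 reads: "The proportion of subjects with hemoglobin within 10-11 g/dL in US and 10-12 g/dL in Ex-US will be analyzed using logistic regression model". The bullet it implements, in the same section, is "Proportion of subjects with hemoglobin within 10-12 g/dL averaged over 36 to 44, 44 to 52". SAP 4.3 has "Proportion of subjects with Hb within 10-12 g/dL averaged over Weeks 28 to 36, 44 to 52, and 96 to 104". The US line of SAP 11.2.2.1 adds "and patients with mean hemoglobin level between Hb 10-12 g/dL". Protocol 3.2.3 has "Proportion of subjects with 10-12 g/dL averaged over Weeks 28 to 36, 44 to 52, and the final 8-weeks of treatment". The only other place where a US range of 10 to 11 appears is background: protocol 2.2 notes that ESA labeling "directs prescribers to target Hb levels of 10 to 11 g/dL in the US and 10 to 12 g/dL outside the US".

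**The concern.** SAP 11.1.1.1 is where a programmer will look for the terms of the primary model. Someone working from that list fits the MI-ANCOVA and MMRM without region; someone working from SAP 5.4 includes it. The SAP does not say which governs. Protocol 9.6 says that significant changes from the protocol's analyses will be highlighted in the SAP, and nothing in the SAP text supplied flags or justifies dropping region. In an open-label non-inferiority trial the terms of the primary model should have one reading before data are analysed, and a factor used to stratify the randomization normally belongs in the analysis.

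The band conflict has a similar cause but lower stakes. One endpoint has two US definitions, and they give very different response rates. The averaging windows also disagree: the 11.3.1.1 bullet starts at Weeks 36 to 44, while SAP 4.3 and protocol 3.2.3 start at Weeks 28 to 36.

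**Working it through.** **1. The plan's own figure.** Inputs from SAP 5.1: true difference -0.30, margin 0.75, SD 1.25 g/dL, at least 600 subjects at 1:1. From SAP 11.1.1.1: two-sided 95% CI.
- SE = 1.25 × √(2/300) = 0.1021.
- (0.75 − 0.30)/0.1021 = 4.41; 4.41 − 1.96 = 2.45; power = Φ(2.45) = 99.3%.

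The stated figure of at least 99% reproduces. Neither region nor the band enters this formula.

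**2. Factors in the primary Hb model, side by side** (screening Hb is excluded from the Hb models in both documents).

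| Source | CV history | Epoetin dose | Region | Incident dialysis |
|---|---|---|---|---|
| Protocol 9.4.3.1 | yes | yes | yes | no |
| SAP 5.4 | yes | yes | yes | yes |
| SAP 11.1.1.1 | yes | yes | no | yes |

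Adding incident dialysis is stated in both SAP sections. Dropping region happens only by omission.

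**3. What adjusting for region would do.** The documents give neither the US share nor the regional shift in Hb change, so both are assumed: US share 50%, shift d from 0.25 to 1.0 g/dL. Region then explains 0.5 × 0.5 × d² of the variance 1.25² = 1.5625.
- Half-width = 1.96 × √(1.5625 − 0.25d²) × √(2/300).
- No adjustment: 1.96 × 1.25 × 0.08165 = 0.200.
- d = 0.25: residual SD 1.244, half-width 0.199.
- d = 0.5: residual SD 1.225, half-width 0.196.
- d = 1.0: residual SD 1.146, half-width 0.183.

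The planned distance to the margin is 0.45 g/dL. Allocation is 1:1 within region by design, so omitting the term should leave the treatment estimate close to unchanged and, if anything, widen the interval slightly.

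**4. What the band does within one arm.** Assume normally distributed average Hb, centred on 11.0, because roxadustat is titrated "in order to maintain a Hb level of approximately 11 g/dL". The documents give no SD for achieved Hb, so a range is shown; 1.25 is the planning SD for Hb change.

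| SD | Within 10-11 | Within 10-12 |
|---|---|---|
| 0.5 | 48% | 95% |
| 0.7 | 42% | 85% |
| 0.9 | 37% | 73% |
| 1.25 | 29% | 58% |

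At a mean of 11.0 the ratio is exactly one half by symmetry. Over assumed means of 10.5 to 11.25 and SDs of 0.8 to 1.25, the narrower band gives 26% to 47% and the wider one 54% to 79%. The narrower band then captures 42% to 67% of the subjects counted by the defined endpoint.

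**The case against.** **On region.** SAP 5.4 can be read as settling the matter, since it names the randomization factors as model terms. The short list in SAP 5.1 could be a bullet lost when the PDF was read, so it is weak evidence alone. Both points stand, and they limit the finding to an inconsistency: the SAP does not uniformly exclude region. They do not account for SAP 11.1.1.1, a separate list written for the efficacy analyses in which incident dialysis takes the fourth place.

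A reader might infer that leaving region out endangers the primary result. The documents do not support that, given stratified 1:1 allocation, about 99.3% power at 600 subjects and the small precision effect shown above.

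A reader might also infer that the plan needs a new by-region analysis, because roxadustat has one target everywhere while "Epoetin dose adjustments during the Treatment Period should be based on country-specific epoetin alfa Package Insert or SmPC". SAP 13 already permits efficacy analyses by stratification factor, and the list in SAP 11.1.3 is itself optional. Protocol 9.7 also tolerates epoetin dosing outside the label, so the size of any regional gap is unknown. A region main effect would not reveal such a gap in any case.

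**On the band.** The endpoint is an additional one, outside the fixed sequence of SAP Table 6, and SAP 11.2.2.1 already plans a US 10-12 proportion for Weeks 28 to 52. A US result on the wider band is therefore planned whichever reading is used here. The 10-11 band may be a deliberate analysis based on the US label, but no such endpoint is defined. The SAP mostly uses US and Ex-US to mean submissions (4.1, 4.2, 11.1.3, 11.2.2.1), so it is unclear whether the sentence refers to the US submission or to subjects located in the US.

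A reader might infer that the choice of band reverses the comparison between arms. With roxadustat at 11.0 and epoetin at an assumed 10.5, it would: −20.5 to −2.3 points on 10-11 and +11.5 to +3.6 on 10-12, across SDs of 0.5 to 1.25. But the documents give no epoetin mean. With epoetin at 11.3, which follows from the planning difference of −0.30, both bands favour roxadustat (+20.8 to +3.2 and +4.0 to +1.3).

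**Conclusion.** The region point holds as an inconsistency in the specification of the primary model. SAP 11.1.1.1 omits a randomization factor that protocol 9.4.3.1 includes and SAP 5.4 brings in. It should be corrected because doing so costs almost nothing and leaves one primary model. The expected precision gain is small, at most 0.017 g/dL of half-width under the assumptions above, and no change in the primary conclusion is claimed.

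The band point holds as a minor wording error in an additional endpoint. It does not touch the primary test, the power or the fixed sequence. Its effect on the reported US response rate could be large (a halving if mean Hb is 11.0), but that figure rests on assumed means and SDs. The window mismatch is a plain text conflict and needs no assumption.

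**What to change.** **Main change.** Add geographical region (US vs Ex-US) to the factor lists in SAP 5.1 and 11.1.1.1 and keep incident dialysis. The MI-ANCOVA and MMRM then carry cardiovascular history, epoetin dose, region and incident dialysis, in line with the randomization, the protocol and SAP 5.4. If region is to be left out on purpose, say so and give the reason. Cost: two lines of text and one model parameter.

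**Minor change.** In the model sentence of SAP 11.3.1.1, use 10-12 g/dL for both submissions, and align the first averaging window with SAP 4.3. The bullet for Hb of at least 10 g/dL next to it has the same window mismatch and should be aligned too. If a 10-11 label band is wanted, define it in SAP 4.3 as a supplementary endpoint, report it beside 10-12, and state whether US means the US submission or subjects located in the US. Cost: wording only, plus one extra model run if the supplementary endpoint is kept.
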